Informed Consent	x							
Psychological Interview (SCID)	x							
Physical Exam		x						
fMRI Session			x			x		
Pulse Oximetry			x			x		
Lupron injection			x		x			
Venipuncture		x	x			x		
Self-Report Questionnaires								
Daily Rating Form	x	x	x	x	x	x	x	x
IDAS-II	x		x	x	x	x	x	x
BITe	x		x	x	x	x	x	x

Misophonia questionnaire	X		X	X	X	X	X	X
SNAP	X							
Demographic Questionnaire	X							
Trauma History Questionnaire	X							
Handedness Questionnaire	X							
Hormone History Questionnaire	X							
BIS/BAS	X		X			X		
COVID Stress Scale (CSS)			X			X		
Behavioral Tests								
Visual Dot Probe			X			X		
Point Subtraction Aggression			X			X		

Note: H/G = Hypogonadism; W/D = Withdrawal; F/U = Follow-up

Participants. Healthy, euthymic, unmedicated (including oral contraceptives), 21-45-year-old women with regular menstrual cycles and either with or without a history of PND will be recruited from an existing research registry of euthymic women with and without a history of PND screened for [name] and [name]'s last NIH-sponsored study and with the social media advertising pipeline used for the last study. All women will have one or more biological children and will be at least one year past their most recent childbirth. In order to maximize the likelihood of identifying HS+, those with a history of PND must have a history of at least one episode of DSM-V major depression accompanied by irritability, with an onset within six weeks postpartum (Forty et al., 2006), and no history of DSM-V major depression with an onset outside of the postpartum period. In order to maximize the likelihood of identifying HS-, the control group will comprise women without a history of any past or present psychiatric disorder, including PMDD, and without first-degree relatives with a history of PND. Additional inclusion and exclusion criteria required for participant safety are detailed in the human subjects section. Hormone sensitivity will be prospectively assessed using the hormone protocol described below.

We have defined HS+ as a 30% or greater change in any of the IDAS-II mood scales, which include dysphoria, suicidal ideation, ill temper (i.e., irritability), and wellbeing (i.e., reverse-keyed) during hormone addback or withdrawal, compared with the individual's own baseline using the equation below:

$$\% \text{ symptom change} = (\text{Addback score} - \text{Baseline score}) / \text{Baseline score}$$

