Our target number of subjects to include in the fMRI analyses is N=30 (15 confirmed HS+ and 15 confirmed HS-). Because we have not yet identified a mechanism by which we can predict hormone sensitive status at baseline with 100% accuracy, we will need to over-recruit women with a history of PND to account for those who end up not being HS+. In our previous study 11 of the 15 women (73%) with a history of PND were HS+. For the current study, we therefore plan to over-enroll women with a history of PND in order to reach our target of 15 women with confirmed HS+. If 73% of women with a history of PND and no history of non-puerperal major depressive disorder are HS+, then we will need to enroll 21 women to find 15 with confirmed HS+. Based on the 9% dropout rate of our prior trial, we estimated a 9% dropout rate, and as such, we have budgeted for an additional 3 subjects to account for dropouts. In the prior study 2/3 of the women who withdrew from the protocol had a history of PND, so we anticipate 2 women with a history of PND and 1 control (without a history of PND) will withdraw from the proposed study. These numbers are summarized in the following table:

Recruitment Group	Target Enrollment	Confirmed HS+/HS- (included in fMRI/behavioral analysis)	Not HS+/HS- (excluded from fMRI/behavioral analysis)	Withdrawn
History of PND	23	15 HS+	6 not HS+	2
Control (no history of PND)	16	15 HS-	0 not HS-	1
TOTAL	39	30	6	3

Thus, we plan to enroll a total of 39 subjects (n=16 without a history of PND, n=23 with a history of PND).

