7.2 Statistical Methods

We have defined HS+ as a 30% or greater change in any of the IDAS-II mood scales, which include dysphoria, suicidality, ill temper (i.e., irritability), and wellbeing (i.e., reverse-keyed) during hormone addback or withdrawal, compared with the individual's own baseline using the equation below:

$$\% \text{ symptom change} = (\text{Addback score} - \text{Baseline score}) / \text{Baseline score}$$

Percent symptom change will be calculated for each of the IDAS-II scales listed above at both the addback visit (V6) and withdrawal visit (V7). If a participant has a percent symptoms change of 30% or greater on any of the IDAS-II scales listed, she will be classified as HS+. HS- is defined as less than 30% change in any of the IDAS-II mood scales.

We will only include those with confirmed HS+ and HS- in our planned analyses. Those with a history of PND confirmed to be HS- will be excluded from planned analyses. However, if we have enough subjects with a history of PND who are HS-, then they may be included as a separate group in exploratory analyses. Alternatively, if those with a history of PND who are HS- are not significantly different from those without a history of PND who are HS- in terms of our key outcome variables, then we will pool the groups to increase power.

The IDAS-II is scored using a 5-point Likert scale, ranging from 1 "Not at all" to 5 "Extremely." The scales we will use to determine hormone sensitivity and their ranges are listed in the table below:

IDAS-II Scale	Minimum Score	Maximum Score
Dysphoria	10	50
Suicidality	6	30
Ill Temper	5	25
Wellbeing	8	40

Missingness. We will use multiple imputation to correct for data determined to be missing at random, given that it is a reliable method for obtaining valid inferences in both behavioral and fMRI research (Rubin, 1987; Vaden et al., 2012). Data for dropouts will be compared with data for those who complete

the study to determine the extent to which excluding their data will introduce selection bias, and selection bias will be identified as a weakness in any resulting publications or presentations.

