7.3 Subject Population(s) for Analysis

The rationale for the proposed study is that employing a scaled down model of puerperal hormonal events permits the identification of a group of individuals homogeneous for hormone sensitivity (HS+),

hence creating the best opportunity for disentangling the specific changes in brain function due to reproductive hormones (i.e., HS-) from those accompanying reproductive hormone-precipitated affective dysfunction (i.e., HS+). Thus, we will only include those with confirmed HS+ and HS- in our planned analyses as described in section 7.2.

8 Safety and Adverse Events

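### As tabulated, the planned HS+ versus HS- contrast cannot separate hormone sensitivity from a response to hormones that depends on PND history, and the women who could help separate them are excluded or pooled on a non-significant test

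*Combined protocol and SAP*

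**What the plan says.** Section 6 (Participants) recruits two contrasting groups. Women with a PND history must have had postpartum major depression with irritability and no major depression outside the postpartum period. For the others, "In order to maximize the likelihood of identifying HS-, the control group will comprise women without a history of any past or present psychiatric disorder"; a first-degree relative with PND also rules a control out.

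The Section 7.1 table takes all 15 HS+ women from the PND group and all 15 HS- women from the controls. It expects 6 PND women who are not HS+ and 0 controls who are not HS-, under a column headed as excluded from the fMRI and behavioral analysis.

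Section 7.2 derives HS status from visits 6 and 7. On PND women who prove HS-, it says "Those with a history of PND confirmed to be HS- will be excluded from planned analyses". It then allows them as a separate exploratory group if there are sufficient numbers, without giving a number. Alternatively, if they do not differ significantly from control HS- women on the key outcomes, "then we will pool the groups to increase power".

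The models in Section 7.2 have no PND-history term. Section 7.3 presents the design as isolating a homogeneous hormone-sensitive group, "hence creating the best opportunity for disentangling the specific changes in brain function due to reproductive hormones" from those that accompany hormone-precipitated affective dysfunction.

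**The concern.** If the table is realised, hormone sensitivity and PND history are the same variable in the 30 women analysed. A larger change from baseline to addback in HS+ could reflect hormone sensitivity. It could equally reflect a response to hormones found in women with past PND whether or not their mood changes under the challenge. The planned model cannot choose between these, although Section 7.3 interprets the contrast as the first.

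The PND HS- women share the history of the HS+ group and the HS status of the controls, so they bear directly on the question. Their scans and tasks at visits 3 and 6 are complete when they are classified. Leaving them out, or letting an outcome test decide whether they join the controls, gives up information already collected. The pooling route also lets the primary endpoints determine who is in the comparison group.

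**Working it through.** **Inputs.** From Section 7.1: 15 per group, d=1.10 with 80% power, HS+ rate 11/15 in PND women, two PND and one control withdrawal. From Section 7.2: alpha .05, and Bonferroni correction with the number of tests not stated. Assumed here: two-sided tests; four primary tests where a Bonferroni figure is shown.

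**1. The plan's own figures.**
- Enrolment: 15/(11/15) = 20.5, rounded up to 21; 21 − 15 = 6 PND HS-; 21 + 2 = 23; 15 + 1 = 16; 23 + 16 = 39. This matches.
- Power, two-sample t on change scores: noncentrality 1.10 × √(15×15/30) = 3.01 on 28 df, giving 83%; 80% power is reached at d=1.06. The stated 80% at 1.10 is slightly conservative.

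**2. Can the two factors be separated?**
- Planned data, columns intercept, HS, history: the last two are identical for all 30 women, so the rank is 2 of 3. The same holds for HS × phase and history × phase. Adding history as a covariate would not help, because it is not estimable.
- If history alone shifted the hormone response by d=1.10 and HS had no effect, the planned contrast would be significant with the same 83% probability.
- With the 6 PND HS- women added, the rank is 3 of 3.

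**3. Precision of the within-PND contrast (15 versus 6).**
- Standard error: √(1/15 + 1/6) = 0.483 SD, against √(2/15) = 0.365 SD for 15 versus 15.
- 95% interval half-width: 2.093 × 0.483 = 1.01 SD, against 2.048 × 0.365 = 0.75 SD.
- Power at d=1.10: noncentrality 1.10 × √(15×6/21) = 2.28 on 19 df, giving 58%; 80% needs d=1.43.
- At alpha .05/4 = .0125: 34%, against 64% for 15 versus 15.
- The count is uncertain. With 21 PND completers and an HS- rate of 4/15, six or more has probability about 50%, and three or fewer about 15%.

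**4. The pooling gate (6 PND HS- versus 15 control HS-).**
- One test at alpha .05: power 35% at d=0.8 and 58% at d=1.10, so it is non-significant in 65% and 42% of cases.
- The gate refers to the key outcomes in the plural. For four independent outcomes, each truly differing by d=0.8, all are non-significant in 0.65⁴ = 18% of cases. With correlation 0.5, simulation gives about 34%. At alpha .0125 the figures are about 49% and 60%.
- Pooling would dilute a pure history effect of 1.10 to 1.10 × (1 − 6/21) = 0.79. It would not remove it.

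**5. Consistency.** The hypothesis-testing paragraph of Section 7.2 says non-significant tests will be reported as inconclusive. The pooling rule in the same section uses a non-significant test as grounds to merge two groups.

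**The case against.** Several stronger readings are tempting, and the documents do not support them.

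- A reader might infer that any HS+ versus HS- difference could be left over from past depression. The hypotheses concern change from baseline to addback, and Appendix C names the interaction as the principal effect. Stable differences between women therefore cancel. What remains is a history-dependent response to the hormones. The cancellation does not extend to the group comparisons at each time point that Appendix C also plans.
- A reader might infer that PND HS- women are the only ones who could separate the factors. HS+ controls could too. The table expects none and its column heading would exclude them, but the exclusion sentence in Section 7.2 names only PND women.
- A reader might infer that the plan ignores the PND HS- women. It already permits an exploratory group; the weakness is that this is optional and has no threshold.
- A reader might infer that the pooling gate would usually be passed when the groups differ. That is true of one test at d=0.8, but not in general, as the four-outcome figures show.

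It can also be said that recruiting contrasting groups is deliberate, that excluding non-puerperal major depression narrows the rival explanation, and that hypotheses 1c and 2c are tested within HS+, where history is constant as tabulated. These points stand, but 1c and 2c are secondary and the plan says it is not powered for them. It is also fair that conditioning the analysis on a minimum count is defensible for a test. It is less so for an estimate, whose interval shows how little a small group can say.

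**Conclusion.** The concern holds in this limited form. With the tabulated groups, hormone sensitivity and PND history are completely aliased in the planned interaction, so the primary contrast alone cannot attribute a difference to hormone sensitivity. This rests on the Section 7.1 projection of 15, 15 and 0; HS+ controls, if they occurred and were analysed, would weaken the aliasing.

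The pooling option is a separate defect. It makes the HS- group depend on the outcomes and conflicts with the plan's own reading of non-significance. How often it would be triggered depends on the number of outcomes, their correlation and alpha.

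The within-PND contrast makes an HS effect within PND history estimable but does not test it with adequate power: 58% at d=1.10 unadjusted, about 34% under Bonferroni for four assumed tests. It is free only of PND history as a yes/no factor. Severity or number of past episodes may still differ, and HS status is observed, not randomised. None of this makes the primary contrast invalid as a comparison of the two recruited groups.

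**What to change.** - Keep the primary HS+ versus HS- contrast and the sample size.
- Delete the option to pool PND HS- women with controls after a non-significant comparison.
- Prespecify for each primary endpoint a secondary estimation analysis that keeps PND HS+, PND HS- and control HS- as separate groups. Report PND HS+ versus PND HS-, and PND HS- versus control HS-, with confidence intervals.
- Say how HS+ controls will be handled, so that the Section 7.1 table and the Section 7.2 text agree, and report any as their own group.
- State in Sections 7.2 and 7.3 that the primary contrast alone cannot attribute a difference to hormone sensitivity rather than PND history.

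The cost is a little more analysis of data already collected, with no added scans or participants. The intervals will be wide, about ±1.01 SD with six PND HS- women and wider with fewer, and should be presented as estimation. The change should be made before outcomes are examined by group.

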Percent symptom change will be calculated for each of the IDAS-II scales listed above at both the addback visit (V6) and withdrawal visit (V7). If a participant has a percent symptom change of 30% or

greater on any of the IDAS-II scales listed, she will be classified as HS+. HS- is defined as less than 30% change in any of the IDAS-II mood scales.

We will only include those with confirmed HS+ and HS- in our planned analyses. Those with a history of PND confirmed to be HS- will be excluded from planned analyses. However, if we have enough subjects with a history of PND who are HS-, then they may be included as a separate group in exploratory analyses. Alternatively, if those with a history of PND who are HS- are not significantly different from those without a history of PND who are HS- in terms of our key outcome variables, then we will pool the groups to increase power.

Hormone Administration. The hormone administration protocol shown in **Figure 6** and described below will be administered in a double-blind manner and replicates the methods of our recent study and Bloch et al (2000), modified as follows: the hormone addback period is truncated and the hormone doses have been reduced based on our finding that HS+ can be distinguished from HS- after two weeks of low-dose addback (see Preliminary Data). To clarify double-blinding, all statisticians in the study will be blinded to the treatment intervention given to participants. As all participants will be completing digital behavioral tasks and self-report questionnaires throughout the study, which will be analyzed upon study completion.

Baseline. Prior to medication administration, participants will complete a physical exam and comprehensive psychological assessment, including interviews and self-report questionnaires. The first fMRI session will be completed during a period of low reproductive hormone levels (days 4-8, the mid-follicular phase), which will be confirmed using a plasma estradiol assay. Conducting the baseline fMRI session during the midfollicular phase promotes consistency in hormone profiles across participants and provides the optimal contrast for affective symptoms during the period of reproductive hormone addback.

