Sensitivity Analysis. In addition to the statistical tests described below, we will use sensitivity analyses to evaluate the robustness of the study's main results to reasonable perturbations of the statistical methods and assumptions used and to help ensure reproducibility of the main results. Sensitivity analysis will address the inclusion/exclusion of questionable data values (i.e., outliers), the use of alternative methods of coping with missing values and dropouts, and modeling assumptions.

Hypothesis testing. We have detailed both the null and alternative hypotheses we will test below. For all hypothesis tests, we will use the Bonferroni method to correct for multiple comparisons. All hypothesis tests that are observed to be not statistically significant will be reported as being inconclusive. In accordance with the ICMJE and Consort Statement, all statistical estimates of population parameters will be tabulated along with confidence intervals. The interpretation of confidence intervals will be an integral part of the data analysis in concert with the statistical hypothesis tests.

Power calculations overview. We have based our power calculations on previous studies of similar effects (i.e, not pilot studies) with N greater than or equal to 30. Given that prior literature suggests large effect sizes for Aims 1 and 2, we believe that point-estimates will yield relatively accurate power calculations.

Aim 1: To determine the extent to which irritability is characterized by dysfunctional threat processing during reproductive hormone challenge relative to baseline in HS+ and HS-.

Null hypothesis 1: HS+ is not characterized by behavioral activation in the context of potential threat during periods of hormone change in the target population.

Alternative hypothesis 1: HS+ is characterized by behavioral activation in the context of potential threat during periods of hormone change in the target population. Given this hypothesis, we will test the following sub-hypotheses:

Null hypothesis 1a: HS+ is not characterized by threat attention bias during hormone addback relative to baseline in the target population.

Alternative hypothesis 1a: HS+ is characterized by threat attention during hormone addback relative to baseline in the target population.

Independent variables: Group (HS+ versus HS-) and Phase (Visit 3-baseline versus Visit 6-hormone addback)

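### Sections 6 and 7.2 exclude HS- women with a PND history, then allow pooling them with control HS- women if the outcomes do not differ significantly, so outcome data could choose the reference group

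*Combined protocol and SAP*

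**What the plan says.** Section 7.2 first gives a fixed rule: "Those with a history of PND confirmed to be HS- will be excluded from planned analyses". If there are enough of these women (no number is given), "then they may be included as a separate group in exploratory analyses". The next sentence offers another route. If these women show no significant difference from the control HS- women "in terms of our key outcome variables, then we will pool the groups to increase power". Section 6 (Study Procedures, Participants) carries the same text.

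Section 7.3 does not choose between these options. It refers back: "Thus, we will only include those with confirmed HS+ and HS- in our planned analyses as described in section 7.2".

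Two general rules in Section 7.2 bear on the point. On multiplicity: "For all hypothesis tests, we will use the Bonferroni method to correct for multiple comparisons". On non-significance: "All hypothesis tests that are observed to be not statistically significant will be reported as being inconclusive".

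The enrolment table in Section 7.1 expects 15 HS+ and 6 not HS+ among women with a PND history who complete, and 15 HS- among controls. It lists the 6 as excluded from the fMRI and behavioral analysis.

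**The concern.** The plan leaves two possible reference groups, 15 women or about 21, and the choice between them depends on outcome data. The stated purpose of increasing power points to the planned HS+ v HS- comparison. But the sentence opens as an alternative to an exploratory use, so its scope is open.

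The rule does not say which variables are the key outcomes, what alpha or margin applies, whether baseline, addback or change is compared, or whether the decision is made per outcome or jointly. It also treats a non-significant result as evidence of sameness, while the same section calls such results inconclusive.

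The two HS- groups are recruited differently. Section 6 requires controls to have no past or present psychiatric disorder and no first-degree relative with PND. The other women have had postpartum major depression with irritability. A real difference between them is plausible. If there is one, pooling moves the HS+ v HS- estimate in a direction that depends on where these women fall, and the stated alpha and confidence intervals take no account of it.

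**Working it through.** **The plan's own figures.** Section 7.1: 15/0.73 = 20.5, so 21 women with a PND history; 21 − 15 = 6 HS-. This reproduces. The stated 80% power at 1.10 SD with 15 per group recomputes as 82.8% (two-sided t-test, alpha .05). The stated figure is slightly conservative, which does not affect this point.

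**Power of the pooling test, 6 v 15.** Two-sided t-test, df = 19, noncentrality d·√(6·15/21) = 2.07d. The .0125 column assumes Bonferroni over four outcomes (.05/4), one for each primary endpoint listed in the Appendix C overview. The chance that all four are non-significant, if independent with the same gap, is (1 − power)⁴.

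| True gap (SD) | Power at .05 | Power at .0125 | All four n.s. at .05 | All four n.s. at .0125 |
|---|---|---|---|---|
| 0.5 | 17% | 6% | 48% | 78% |
| 0.8 | 35% | 17% | 18% | 49% |
| 1.1 | 58% | 34% | 3% | 19% |

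Reaching 80% power needs a gap of 1.43 SD at .05, or 1.76 SD at .0125. The 95% interval half-width is t(.975, 19)·√(1/6 + 1/15) = 2.093 × 0.483 = 1.01 SD, nearly the 1.10 SD effect the study is sized on.

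**Consequence for the main comparison.** At least 80,000 simulated trials per scenario; n = 15 HS+, 15 control HS-, 6 PND-history HS-; unit-SD change scores; main test at .05. Assumed here: true HS+ effect 1.10 SD, and PND-history HS- women 0.8 SD toward HS+ on four independent outcomes.

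| Rule | Share pooled | Mean estimate | Power |
|---|---|---|---|
| Always exclude | 0% | 1.10 | 83% |
| One outcome, .05 | 65% | 1.00 | 77% |
| One outcome, .0125 | 84% | 0.94 | 73% |
| All four, .05 | 18% | 1.07 | 81% |
| All four, .0125 | 49% | 1.01 | 77% |
| Always pool | 100% | 0.87 | 68% |

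The last row follows by hand: the reference mean shifts by (6/21) × 0.8 = 0.23, and 1.10 − 0.23 = 0.87. Coverage of the 95% interval under the four conditional rules is 91.3% to 94.2%; always pooling gives about 91%. With outcomes correlated 0.3, the all-four rule at .05 pools 27% of the time (estimate 1.06, power 81%).

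**Type I error.** With no HS+ v control difference and a 0.5 SD shift in the PND-history HS- women, the conditional rules reject in 6.1% to 6.9% of trials; always pooling rejects in 6.5%. When the two HS- groups match, the conditional rules reject in 5.2% to 5.5%.

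**What pooling could gain.** At 1.10 SD, 15 v 21 instead of 15 v 15 raises power from 82.8% to 88.5% at .05, and from 64% to 73% at .0125, but only if the two HS- groups truly match.

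**The case against.** The strongest objection is scope. Exclusion is stated in Sections 6 and 7.2, the Section 7.1 table repeats it, and the target is N=30. Pooling is introduced as an alternative to an exploratory use, so it may itself be exploratory. On that reading the primary reference group never changes and the simulations are moot. This reading is possible, but the text does not establish it, and the stated aim of increasing power points the other way.

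Second, some gaps are smaller than they look. Appendix C lists four primary endpoints, the power statements use alpha .05, and Bonferroni is said to cover all tests. What is missing is any link from these to the pooling decision. The inconclusive standard is also worded as a reporting rule, so the conflict with it is one of logic more than of letter.

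Third, most of the distortion comes from mixing unlike groups and little from testing first: 6.5% rejection for always pooling against 6.1% to 6.9% for the conditional rules. That is correct.

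Fourth, the 0.8 SD shift toward HS+ is assumed. With a shift of 0.5 SD away from HS+, the conditional rules give mean estimates of 1.15 to 1.22 and power of 87% to 93%. The t-test model is also only a stand-in for the voxel-wise analysis of 1b and the multi-factor ANCOVA of 2b. These points limit the size of the effect. They do not supply the missing definition of the reference group.

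**Conclusion.** The concern holds. The rule is written in advance, so it is not post hoc, but its trigger is outcome data, its terms are undefined and its scope is unclear. Two analysts could follow the plan faithfully and report different HS+ v HS- results.

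If the rule governs the planned comparison, a test that misses a 0.8 SD gap about two times in three at alpha .05 would choose the reference population. The numerical effect is modest: a shift of 0.03 to 0.16 SD in the mean estimate in the 0.8 SD scenario, and one to two points of excess type I error with a 0.5 SD shift. These sizes rest on the assumed gaps, unit-SD change scores and a main test at .05. The low power of a 6 v 15 comparison needs only the plan's expected numbers and a two-sided t-test. The plan should be changed on this point.

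**What to change.** Delete the conditional pooling sentence in Sections 6 and 7.2. State that the primary comparison is the set in the Section 7.1 table, HS+ women with a PND history v control HS- women, whatever any preliminary test shows. This wording also makes explicit that a control woman who meets the HS+ definition is outside the primary set, as the table's excluded column implies. Always including the PND-history HS- women would equally remove the dependence on outcomes; exclusion is proposed because Sections 7.1 and 7.2 already state it.

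For each primary endpoint, always report one pre-specified sensitivity analysis that adds all PND-history HS- women to the HS- group (about 15 v 21). Do not include PND history as a covariate in it. With that covariate the three-group model is saturated, and the HS effect reduces to HS+ v the 6 PND-history HS- women: 60% power at 1.10 SD, and 80% only at about 1.4 SD. Report the PND-history HS- minus control HS- difference with its 95% interval and attach no decision to it.

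The cost is wording in two places plus one sensitivity analysis and one contrast per primary endpoint, with no new data. The power gain shown above is forgone.
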